STUDY DESIGN	
The study is a monocular (only OD measured, matching type of correction for OS), subject masked, 2 x 2 randomized, crossover (with an additional non-randomized baseline reference (3 arms in all)) comparing the within-lens difference in diurnal (AM to PM) change in optical quality with different soft lenses relative to the diurnal change at baseline (no lens).
 
Subjects will be tested for and must meet all inclusion criteria and not meet any exclusion criteria prior to beginning lens testing.
 
Lens wearing protocol:
 
 1. Subjects will first have measurements acquired every 2 ± 0.5 hours for 12 hours without any lenses (no lens, baseline). The subject will wear their habitual spectacles between measurement periods. 2. Following a day of washout with spectacle wear only each type of lens will be used in both eyes for a period of 2 ± 1 days. Early the following morning, the subject will present to the clinic wearing spectacles. A lens of the same type they have been wearing for the previous 2 ± 1 days will be inserted while a masked examiner then performs measurements every 2 ± 0.5 hours for 12 ± 1 hours. Measurements will include monocular aberrometry (minimum 5mm analysis diameter), Medmont topography, and subjective measures. (0-100 scale). 3. Subjects will then be dispensed the next randomized lens pair and told to not wear the lens that day or the following (washout) day, but the next 2 ± 1 days. As previous, the subject will present to the clinic on the third day not wearing the lenses. Lenses will be inserted, and then measures will be taken throughout the day. 
Measurement protocol:
 
 1. At the beginning of each testing day, measures of the subject's eye alone will be captured. This will serve as 'baseline' for each day. 2. The study lenses will then be inserted according to the lens randomization schedule. 4. Following 10-20 minutes of lens settling, eye+lens aberrometry (minimum 5mm analysis diameter) and subjective measures (0-100 scale) will be acquired. 3. This cycle will be repeated every 2 ± 0.5 hours up to 12 ± 1 hours. 4. At the end of 12 ± 1 hours, the subject will return all lenses of that set, and be given the next set of lenses to repeat the washout, wearing, and measurement cycle. 
Dilation Protocol:
 
No pharmacological dilation will be used in this study. Subjects will be in a dark room aiming to achieve a natural pupil diameter of at least 5 mm. Upon inclusion, if a subject cannot

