The study is a monocular (OD only), subject masked, 2 x 2 randomized, crossover (with an additional non-randomized baseline reference (3 arms in all)) comparing the difference in diurnal change in optical quality with different soft lenses relative to baseline (no lens).

Lens wearing protocol:

1. Subjects will first have measurements acquired every 2 ± 0.5 hours for 12 ± 1 hours without any lenses (no lens, baseline). The subject will wear their habitual spectacles between measurement periods.
2. Following a day of washout with spectacle wear only, each type of lens will be used in both eyes for a period of 2 ± 1 days. Early the following morning, the subject will present to the clinic wearing spectacles. A lens of the same type they have been wearing for the previous few days will be inserted while a masked examiner then performs measurements every 2 ± 0.5 hours for 12 ± 1 hours.
3. Subjects will then be dispensed the next randomized lens pair and told to not wear the lens that day or the following (washout) day, but the next two days. As previous, the subject will present to the clinic on the third day not wearing the lenses. Lenses will be inserted, and then measures will be taken throughout the day.

Measurement protocol:

1. At the beginning of each testing day, aberrometry, Medmont topography (non-invasive tear break-up), and subjective quality measures of the subject's OD eye alone will be captured. This will serve as 'baseline' for each day.
2. The study lenses will then be inserted according to the randomization schedule.
3. Following 10-20 minutes of lens settling, eye+lens aberrometry (minimum 5 mm analysis diameter, Medmont corneal topography, and subjective (0-100 scale) measures will be acquired on the OD. Measures of contact lens position (through recorded imaging) will also be performed. Measures at this time point will serve as "time 0" for each lens wearing day.
4. This cycle will be repeated every 2 ± 0.5 hours up to 12 ± 1 hours.
5. At the end of 12 ± 1 hours, the subject will return all lenses of that set, and be given the next set of lenses to repeat the washout, wearing and measurement cycle.

Dilation Protocol:

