No pharmacological dilation will be used in this study. Subjects will be in a dark room aiming to achieve a natural pupil diameter of at least 5 mm. Upon inclusion, if a subject cannot achieve a non-dilated pupil diameter of at least 5 mm, they will be excluded from the study. If a subject meets a 5 mm pupil on most time points/lenses, but not all, inclusion of data acquired smaller than 5 mm will be scaled to 5 mm and considered on an individual basis.

Equipment:

1. An aberrometer (e.g. COAS-HD or CSO Osiris) will be used for all optical measures. The aberration data will be obtained for central 3- and 5-mm diameter areas. Wavefront data will be reconstructed by both modal (up to 6th order Zernike polynomials) and zonal (local slope) methods.
2. A Medmont corneal topographer will be used following each set of aberration measures to also monitor the tear film upon the eye/contact lens.

SUBJECTSSample Size:

This section describes the rationale and approach used to establish the minimum sample size (N) needed to achieve 80% power at a nominal significance level $\alpha=0.05$ for detecting a mean difference between percentage change in RMS of higher-order wavefront aberrations measured over a 12-hr period for the test lenses and the percentage change observed without a contact lens (no-CL). For each subject and lens, a series of five RMS measurements will be obtained at 0 hours (baseline) and at six, 2-hr intervals within each period. Technically, the statistical power for testing the contact lens main effect will depend not only on the structure of the covariance matrix but also on how the baseline measurements recorded at time=0 hours are incorporated into the statistical model(s). But, given the degree of uncertainty about the input parameter values required to estimate sample size, we believe it reasonable to base initial calculations on a dependent sample t-test on a mean difference score under the assumption of no differential carryover effect. Thus, the target parameter of interest for our primary analysis corresponds to the true difference in the mean post-baseline percentage change over 12 hours between each of the test contact lenses and no-CL for N subjects. Note that this test would be equivalent to testing the interaction of "lens" and "hours of use" factors in a two-way repeated measurements ANOVA.

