1. At the beginning of each measurement day, aberrometry, Medmont topography, and subjective quality measures of the subject's eyes alone (COAS and Medmont) will be captured. This will serve as 'baseline' for each day (for the spectacle day, this will also be "time 0").
2. The study lenses (or no lens for spectacle day) will then be inserted according to the randomization schedule.

3. Following 10-20 minutes of lens settling, the eye+lens aberrometry (minimum 5 mm analysis), Medmont topography, and subjective quality (0-100 scale) measures will be acquired for each eye. This will serve as “time 0” for each lens wearing day.
4. This cycle will be repeated every 2 ± 0.5 hours up to 12 ± 1 hours.
5. At the end of 12 hours, the subject will return all lenses of that set, and be given the next set with a schedule of washout and wear days.

Testing Day 4, Visit 7 = Exit:

1. Exit ocular health (with conjunctival and corneal staining)
2. Exit Snellen visual acuity

STATISTICAL ANALYSIS

[figure not shown]
Separate tables with descriptive statistics will be provided for all baseline, outcome/endpoint and safety variables, as appropriate. Continuous variables will be summarized with location and dispersion parameter estimates while categorical data will be summarized using frequency counts, percentages and margin tables where appropriate. Visualizations and related graphs will be provided in support of these data summaries.

Statistical analyses will be performed only after all data have been collected, transcribed into the electronic database, and error checked and corrected if needed. We will first test for a differential carryover effect of lens using a linear (ANOVA) model. For a crossover design, the model can be expressed as

$$y_{ijkl} = \mu + \alpha_i + \rho_{j(i)} + \gamma_k + \tau_l + \lambda_m + \gamma\tau_{kl} + e_{ijkl}$$

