Second, a comparison of the statistic $\% \Delta_{i(12-0)_{test}}$ for one test lens with $\% \Delta_{i(12-0)_{k-1}}$ the other test lens in the study will be performed by fitting a linear mixed effects regression model with restricted maximum likelihood (REML) estimation. The effect of lens will be parameterized in this model with (0,1) GLM dummy coding using Air Optix with Hydraglide as the reference lens; thus, a separate parameter estimate will be obtained for the other test lens. The initial model will include a single random effect for subject. We will also perform sensitivity analyses by adding covariates and refitting the model with ML to obtain ‘adjusted’ parameter estimates for the fixed effect of lens to account for potential confounding due to measured covariates.

PUBLICATION PLAN:

Work will be presented at least one international meeting, such as American Academy of Optometry, Global Specialty Lens Symposium, ISCLR, BCLA, American Optometric Association, or ARVO. The work will also be prepared for submission for peer-reviewed or trade publication (e.g. Optometry and Vision Science) at Sponsor’s request and if results merit.

TIMELINE: (estimated)

Contract approval: unknown, estimate 1 month

Human subjects approval: 1 month, concurrent to above

Project setup: 1 month, concurrent to above

Recruitment: 1 month, concurrent to above

Data collection: 2 months

Data analysis: 1 month

Report writing: 1 month¹

Contract for 1 year to account for any delays or necessary subsequent analyses.

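### The lens-versus-lens mixed model names no period effect, so any period effect would go into the error term and, with unequal sequences, into the lens estimate

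*Combined protocol and SAP*

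**What the plan says.** The STUDY DESIGN section describes a "2 x 2 randomized, crossover (with an additional non-randomized baseline reference (3 arms in all" in total. Each subject therefore wears the two lenses in a randomised order over two periods, after a no-lens day that always comes first.

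In the Protocol Synopsis, Hypothesis 3 states that Air Optix plus Hydraglyde will vary less over the day than Air Optix Aqua. The second comparison in the STATISTICAL ANALYSIS section addresses this by "fitting a linear mixed effects regression model with restricted maximum likelihood (REML) estimation". Its fixed part is described as follows: "The effect of lens will be parameterized in this model with (0,1) GLM dummy coding", with the Hydraglyde lens as reference. Its random part is "The initial model will include a single random effect for subject". The plan will then "perform sensitivity analyses by adding covariates and refitting the model with ML", but does not list the covariates.

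Period and sequence appear earlier in the same section, in the preliminary step: "We will first test for a differential carryover effect of lens using a linear (ANOVA) model". That model has sequence, subject within sequence, period, lens, carryover and period-by-lens terms. It precedes the lens-versus-no-lens non-inferiority test. Nothing says that its period term is kept for the lens-versus-lens model.

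**The concern.** In a two-period crossover, half the subjects (or nearly half) meet each lens first. If the 12-hour percentage change tends to differ between the first and second lens day, for whatever reason, the within-subject lens difference is shifted up in one sequence and down in the other. A period term removes that shift. Without it, the shift has two effects:

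- It adds to the spread of the within-subject differences, so the standard error is larger than it need be.
- It does not cancel when the two sequences have different numbers of completers, so the lens estimate is biased.

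A finding of no carryover or no period-by-lens interaction does not protect against this, because a plain period effect can exist without either. At stake are the precision and, to a lesser degree, the accuracy of the only randomised contrast in the trial.

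**Working it through.** **Inputs from the plan (SUBJECTS, Sample Size).** SD 2.1%; correlation 0.80; null difference 3.5%; mean difference 2.75%; alpha 0.05; 21 completers, up to 24 enrolled.

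**Reproducing the plan's figure.** The SD of a paired difference is 2.1 × √(2 × (1 − 0.80)) = 2.1 × √0.4 = 1.328 points. The non-centrality is √21 × (3.5 − 2.75)/1.328 = 2.59. A one-sided exact paired t-test then needs N = 21 and has power 0.803, as in Table 1(b); all 15 rows of that table reproduce. The table sizes lens versus no lens. No power is stated for lens versus lens, so carrying 1.328 over to that comparison is an assumption.

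**Effect of omitting period.** Let τ be the true lens difference and P the period 2 minus period 1 difference in the outcome, in percentage points. The within-subject lens difference has mean τ + P in one sequence (n1 completers) and τ − P in the other (n2). With N = n1 + n2:

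- Bias without a period term = P(n1 − n2)/N.
- Expected variance of the differences without a period term = SD_diff² + 4P²·n1·n2/(N(N − 1)).
- With a period term, bias = 0 and SE = (SD_diff/2)·√(1/n1 + 1/n2).
- For equal sequences, the SE ratio is close to √(1 + P²/SD_diff²).

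The documents give neither P nor the allocation ratio or blocking, so P and the splits below are assumed.

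**Standard error, N = 21, split 11/10, SD_diff 1.328.**

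| P (points) | SE without period | SE with period | Bias without period |
|---|---|---|---|
| 0 | 0.290 | 0.290 | 0 |
| 0.5 | 0.311 | 0.290 | 0.024 |
| 1 | 0.366 | 0.290 | 0.048 |
| 2 | 0.532 | 0.290 | 0.095 |

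The balanced formula gives inflation of 7%, 25% and 81% for P = 0.5, 1 and 2. For example, √(1 + 1/1.764) = 1.25.

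**Bias by split.** 11/10: 1/21 = 0.05P. 12/9: 3/21 = 0.14P. 13/8: 5/21 = 0.24P. The completer target is odd, so exact balance is impossible if exactly 21 complete.

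**Sensitivity to the SD.** The plan's 2.1% is √(4.41 × 10⁻⁴) = 0.021 µm read as a percentage. That holds only if higher-order RMS is about 1 µm, and the documents give no mean RMS. With P = 1 and correlation 0.80:

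| Assumed RMS (µm) | SD | SD_diff | SE inflation |
|---|---|---|---|
| 1.0 | 2.1% | 1.33 | √(1 + 1/1.33²) = 1.25, so 25% |
| 0.5 | 4.2% | 2.66 | √(1 + 1/2.66²) = 1.07, so 7% |
| 0.2 | 10.5% | 6.64 | √(1 + 1/6.64²) = 1.01, so 1% |

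**Power and type I error (20,000 simulated trials, two-sided 5%, SD_diff 1.328, assumed lens difference 0.86 points).**

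- Split 11/10: without period, power is 0.81 at P = 0, 0.70 at P = 1 and 0.32 at P = 2. With period it stays at 0.80 to 0.81. Type I error without period is 0.015 at P = 1, so the test is conservative.
- Split 13/8: bias and inflated error partly offset each other. Type I error without period is 0.052 at P = 1, and the mean estimate is 1.10 where the truth is 0.86.

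**Which term matters.** In one simulated data set (12/9, P = 2, true difference 0.86), the REML lens estimate was 1.2587 (SE 0.5263) both with lens alone and with lens plus sequence. Adding period gave 0.9512 (SE 0.2321), with or without sequence.

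**The case against.** The strongest reply has four parts.

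- **The text does not exclude period.** The sentence about the random effect describes an initial model, and the crossover model with period is written out a page earlier. This stands as a limit on wording: the plan names no period term here, which differs from ruling one out. It does not rescue the analysis, because unnamed covariates in a sensitivity model would leave the main estimate without period.
- **The assumed period effects may be too large.** The outcome is a percentage change from each day's own time 0, so a proportional day-to-day shift in RMS cancels. The Sample Size section puts the whole difference between a contact lens and no lens at about 2 points (5% against 3%); a 1-point period effect is half of that. This stands, and the documents offer no evidence that any period effect exists.
- **The SD may be larger than planned.** This also stands and reduces the inflation, as shown above.
- **The imbalance may be small.** Attrition of 5 to 10% of 24 is about 1 to 2 subjects. From 12/12, the worst case is then 12/10, a bias of 2/22 = 0.09P. The 12/9 split needs all three losses to fall in one sequence.

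A reader might also infer that omitting sequence does harm of its own. It does not: with complete pairs, sequence leaves the lens estimate and its standard error unchanged.

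**Conclusion.** The point holds as a cheap improvement to the model. Followed as written, the lens-versus-lens analysis leaves any period effect in the residual. With near-equal sequences, the consequence is mainly lost precision and a conservative test; bias is about 0.05P at 11/10 and 0.14P at 12/9. For a 1-point period effect, the standard error rises by about 25% at a paired-difference SD of 1.33 points, 7% at 2.66 and 1% at 6.64.

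These sizes rest on an assumed period effect, assumed splits, and a planning SD carried over from another comparison and not verified on the percentage scale. What is firm is that no period term is named for this comparison.

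A reader might go further and conclude that the lens comparison is invalid, materially biased or prone to false positive claims. The documents do not support that: they give no period effect, and with near-equal sequences the error is on the conservative side.

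**What to change.** In the lens-versus-lens paragraph of the STATISTICAL ANALYSIS section, state that the REML mixed model for the two lens days has fixed effects for lens and period and a random effect for subject. Sequence may be added by convention.

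The cost is one sentence in the plan and one within-subject degree of freedom (20 to 19 with 21 complete pairs). If there is no period effect, simulated power at 11/10 goes from 0.808 to 0.804. With unequal sequences there is a further small loss: at P = 0 the SE goes from 0.290 to 0.293 at 12/9 and to 0.298 at 13/8. No change to data collection or sample size is needed. Naming the term in advance also removes a choice between two models after the data are seen.

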--------------	--

	
achieve a non-dilated pupil diameter of at least 5 mm, they will be excluded from the study. If a subject meets a 5 mm pupil on most time points of both sets of lenses, but not all, inclusion of data acquired smaller than 5 mm will be scaled to 5 mm and considered on an individual basis.
 
Equipment:
 
 1. An aberrometer (e.g. COAS-HD, CSO Osiris) will be used for all optical measures. The aberration data will be obtained for central 3- and 5-mm diameter areas. Wavefront data will be reconstructed by both modal (up to 6th order Zernike polynomials) and zonal (local slope) methods.
Sample size	Complete N=21, enroll up to N=24
Hypothesis	
 1. The Air Optix plus Hydraglyde lens will have levels of variation in aberration throughout the day not significantly different than the naked eye. 2. The Air Optix Aqua lens will have levels of variation in aberration throughout the day not significantly different than the naked eye. 3. The Air Optix plus Hydraglyde lens will have lower variation in aberration throughout the day relative to the Air Optix Aqua lenses.
TEST COMPARATOR PRODUCTS	
Baseline = Naked eye
 
Lenses: Set of soft lenses
 
 1. Air Optix plus Hydraglyde on daily disposable basis 2. Air Optix Aqua on daily disposable basis (ALCON will provide lenses)
INCLUSION/EXCLUSION CRITERIA	
 1. Habitual prescription within the range of +5.00 D to -6.00 D 2. 18-35 years of age 3. No history of issues of eye alignment or binocularity by self-report 4. No doctor diagnosed, self-reported accommodative or binocular vision issues 5. No doctor diagnosed, self-reported ocular surface disease or dry eye requiring regular, ongoing treatment 6. The subject must appear able and willing to adhere to the instructions set forth in this clinical protocol. 7. Vertex corrected refractive cylinder must be -0.75 or less. 8. Visual acuity best correctable to 20/25 or better for each eye 9. The subject must read and sign the Informed Consent form. 10. No active conditions that may prevent soft contact lens wear. 11. Mesopic pupil size >5.00 mm.
OFF LABEL	No.

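### The adjusted lens-versus-lens sensitivity models switch from REML to ML, making the lens standard error about 2% to 5% too small at N=21

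*Combined protocol and SAP*

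**What the plan says.** The last analysis paragraph of the STATISTICAL ANALYSIS section compares the 12-hour percentage change in higher-order RMS between the two lenses. It uses a "linear mixed effects regression model with restricted maximum likelihood (REML) estimation", with lens as a dummy-coded fixed effect. On the random part it says: "The initial model will include a single random effect for subject".

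The same paragraph then provides for "sensitivity analyses by adding covariates and refitting the model with ML to obtain" a covariate-adjusted version of the lens comparison, whose declared purpose is to allow for confounding by measured covariates. So the estimator changes at the step where the covariates enter, and the stated aim is to estimate the lens effect, not to compare likelihoods.

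The paragraph does not name or count the covariates, does not say whether period is in the model, and gives no degrees-of-freedom method for either fit. It does not say that the adjusted models will be refitted by REML for reporting. The synopsis gives the sample size as "Complete N=21, enroll up to N=24".

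**The concern.** ML divides sums of squares by the number of observations without deducting the degrees of freedom spent on fixed effects; REML makes that deduction. In a trial of about 21 subjects the difference is visible. ML is the right choice when models with different fixed effects are compared by likelihood, but that is not the purpose given here.

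Two things are at stake. The adjusted standard errors, and any intervals or P values built on them, would be somewhat too small. The adjusted and unadjusted results would also differ partly because of the estimator, although the point of the sensitivity analysis is to show what the covariates do. The comparison bears on the third hypothesis in the synopsis, that one lens varies less over the day than the other.

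**Working it through.** **Inputs.** From the documents: 21 completers, up to 24 enrolled (synopsis); two lens days per subject, from the 2 x 2 crossover (STUDY DESIGN); one random subject effect, REML unadjusted and ML adjusted (STATISTICAL ANALYSIS); nominal alpha 0.05 (Sample Size). Assumed, because the plan does not say: k, the number of within-subject fixed effects besides lens, meaning a period term or covariates that differ between a subject's two lens days.

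**The plan's own figure.** N=21 is the row of Table 1(b) with mean difference 2.75 and correlation 0.80. The standard deviation of the difference is 2.1 × sqrt(2 × (1 − 0.80)) = 1.328. The noncentrality is sqrt(21) × (3.5 − 2.75)/1.328 = 2.588. A one-sided paired t-test at 0.05 then has power 0.803, as printed. All 15 rows of the table reproduce in the same way, and 21/(1 − 0.10) = 23.3, which rounds up to 24. N=21 is therefore a sound base for what follows.

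**Ratio of standard errors.** In complete data with two observations per subject and a random intercept, the lens effect is estimated within subjects. ML divides the within-subject sum of squares by N; REML divides it by N − 1 − k. Hence

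SE(ML)/SE(REML) = sqrt((N − 1 − k)/N) = sqrt((20 − k)/21) at N=21.

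The actual level of a nominal two-sided 5% test with a t reference on 20 − k degrees of freedom is 2 × P(T > t(0.975) × ratio).

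| k | Ratio | SE too small by | Actual level, ML with t reference |
|---|---|---|---|
| 0 | sqrt(20/21) = 0.976 | 2.4% | 5.5% |
| 1 | sqrt(19/21) = 0.951 | 4.9% | 6.1% |
| 3 | sqrt(17/21) = 0.900 | 10.0% | 7.5% |
| 4 | sqrt(16/21) = 0.873 | 12.7% | 8.3% |

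REML with the same t reference holds 5.0%. If all 24 completed, the first two shortfalls would be 2.1% and 4.3%.

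**Which covariates count.** Subject-level covariates use no within-subject degrees of freedom in complete data, so they leave k unchanged. Only terms that differ between the two lens days raise it.

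**Check by simulation.** Mixed models were fitted by both estimators to 300 simulated trials per scenario, with N=21, correlation 0.80 and a period term throughout. The median ratios were:

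- no covariates: 0.951 (formula 0.951);
- three subject-level covariates: 0.951 (formula 0.951);
- two subject-level and two lens-day covariates: 0.905 (formula 0.900);
- four lens-day covariates: 0.857 (formula 0.845).

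The formula is close throughout and slightly overstates the shortfall when several lens-day covariates are fitted.

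**Reference distribution.** If the software used a normal reference, the levels at k=0 and k=1 would be 7.0% and 7.8% under ML, against 6.4% and 6.5% under REML. Much of that excess comes from the reference distribution, which the plan leaves open for both models.

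**The case against.** The strongest objection is that little depends on this. The plan labels these fits sensitivity analyses of its second comparison. The unadjusted lens-versus-lens model already uses REML. The comparisons with no lens, and the sample size, rest on a paired t-test. No decision is tied to the adjusted models, and the plan asks them for parameter estimates without mentioning P values or intervals. Checking whether an estimate moves is the usual purpose of such an analysis, and the lens estimate is essentially the same under either estimator. All of this stands, and it makes the point minor. It does not make the estimator right: an adjusted estimate is normally reported with a standard error, and that standard error would be biased.

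A reader might also infer more than the documents support:

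- *That every added covariate shrinks the lens standard error.* It does not. Many of the items collected at entry, such as demographics, refraction and habitual lens use, are subject-level and add nothing to the shortfall in complete data. Such covariates also cannot confound a within-subject contrast in complete data, so the stated purpose does point toward lens-day measures. The protocol collects some (each day's eye-alone baseline, topography, lens position), but the plan does not commit to any.
- *That the shortfall is 10% or more.* That takes three or four lens-day terms, which is an assumption without support in the text.
- *That the adjusted analysis is bound to look more precise than the unadjusted one.* Its standard error also depends on how much the covariates explain and how they relate to lens. The estimator is only one component.

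**Conclusion.** The point holds as a small error in the plan as written. Using ML to report adjusted lens estimates makes their standard error 2.4% too small with lens only or with subject-level covariates, and 4.9% too small with a period term or one lens-day covariate. With a t reference, a nominal 5% test then runs at about 5.5% to 6.1%. These figures assume 21 completers with both lens days observed and the single random subject effect stated in the plan. The 10% to 13% range applies only if three or four within-subject terms are assumed.

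The adjusted and unadjusted intervals would differ partly because of the estimator. The effect is confined to the sensitivity analysis and does not reach the lens point estimates in any material way, the paired t-tests against no lens, or the sample size.

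**What to change.** In the last analysis paragraph of STATISTICAL ANALYSIS, have the adjusted lens estimates reported from REML, the estimator already chosen for the unadjusted model. State a small-sample degrees-of-freedom method, for example Kenward-Roger, for both models, since the plan currently gives none for either. Reserve ML for likelihood comparisons of models with different fixed effects. It would also help to name the covariates in advance and say whether period is in the model, because these determine k.

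The cost is one software option and a sentence or two of text. No new data, visits or subjects are needed.
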